#### **4.3. Exclusion Criteria**

Subjects who meet *any* of the following exclusion criteria are not to be enrolled in this study.

- 1) History or evidence of clinically significant disorder, condition, or disease that, in the opinion of the Investigator or Medical Monitor would pose a risk to subject safety or interfere with the study evaluations, procedures, or completion
- 2) Known brain metastasis or leptomeningeal disease
- 3) Uncontrolled intercurrent illness including, but not limited to, active uncontrolled infection, active or chronic bleeding event within 28 days prior to first dose of study drug, uncontrolled cardiac arrhythmia, or psychiatric illness/social situation that would limit compliance with study requirements as judged by treating physician

- 4) History of seizure, underlying brain injury with loss of consciousness, transient ischemic attack within the past 12 months, cerebral vascular accident and brain arteriovenous malformation are excluded from combination therapy with enzalutamide.
- 5) Myocardial infarction, symptomatic congestive heart failure (New York Heart Association Classification > Class II), unstable angina, or serious uncontrolled cardiac arrhythmia within the last 6 months of Cycle 1 Day 1
- 6) Major surgery, defined as any surgical procedure that involves general anesthesia and a significant incision (ie, larger than what is required for placement of central venous access, percutaneous feeding tube, or biopsy) within 28 days of the first dose of study drug
- 7) Impairment of gastrointestinal (GI) function or GI disease that may significantly alter the absorption of GS-5829, including any unresolved nausea, vomiting, or diarrhea that is Common Terminology Criteria for Adverse Events (CTCAE) Grade > 1
- 8) Minor surgical procedure(s) within 7 days of enrollment, or not yet recovered from prior surgery (placement of central venous access device, fine needle aspiration, or endoscopic biliary stent  $\geq$  1 day before enrollment is acceptable)
- 9) Anti-tumor therapy (chemotherapy, antibody therapy, molecular targeted therapy) within 21 days or 5 half-lives, whichever is longer, of study drug dosing (6 weeks for nitrosoureas, mitomycin C, or molecular agents with  $t_{1/2} > 10$  days); concurrent use of an LHRH agonist is permitted for all subjects and ongoing enzalutamide is required in Group 3.
- 10) History of a concurrent or second malignancy, except for: adequately treated local basal cell or squamous cell carcinoma of the skin; cervical carcinoma in situ; superficial bladder cancer; breast carcinoma in situ; adequately treated Stage 1 or 2 cancer currently in complete remission; any other cancer that has been in complete remission for  $\geq 5$  years
- 11) History of long QT syndrome or whose corrected QT interval (QTc) measured (Fridericia method) at screening is prolonged ( $> 450$  ms). Subjects who screen fail due to this criterion are not eligible to be re-screened
- 12) Prior exposure to bromodomain (BET) inhibitors
- 13) Clinically significant bleeding within 28 days of Cycle 1 Day 1
- 14) Known human immunodeficiency virus (HIV) infection
- 15) HBsAg positive
- 16) HCV antibody positive
- 17) Use of moderate/strong cytochrome P450 (CYP)3A4 inhibitors or moderate/strong CYP3A4 inducers within 2 weeks prior to the first dose of study drug (with the exception of enzalutamide in the combination arms)

---

- 18) Evidence of bleeding diathesis
- 19) History of hemoptysis of  $\geq 2.5$  mL/1 teaspoon within 6 months of Cycle 1 Day 1
- 20) History of high grade esophageal or gastric varices
- 21) Anticoagulation/antiplatelet therapy within 7 days of Cycle 1 Day 1, including low molecular weight heparin, or warfarin.

## **5. INVESTIGATIONAL MEDICINAL PRODUCTS**

### **5.1. Enrollment**

This is an open-label study. All baseline tests and procedures must be completed prior to the administration of the first dose of study drug on Day 1. It is the responsibility of the Investigator to ensure that subjects are eligible for the study prior to enrollment. A subject will be considered enrolled once he or she has started treatment.

### **5.2. Description and Handling of GS-5829 and Enzalutamide**

#### **5.2.1. Formulation**

GS-5829 will be supplied as GS-5829-02 (phosphate salt form of GS-5829) and is available as round, plain-faced tablets containing 1, 5, or 10 mg GS-5829. The 1, and 10 mg tablets are film-coated gray and the 5 mg tablets are film-coated orange.

In addition to the active ingredient, 1, and 10 mg tablets contain the following commonly used excipients: microcrystalline cellulose, lactose monohydrate, crospovidone, magnesium stearate, polyvinyl alcohol, titanium dioxide, polyethylene glycol, talc, and iron oxide black.

In addition to the active ingredient, 5 mg GS-5829 tablets contain the following commonly used excipients: microcrystalline cellulose, lactose monohydrate, crospovidone, magnesium stearate, polyvinyl alcohol, titanium dioxide, polyethylene glycol, talc, FD&C yellow #6, and iron oxide yellow. Refer to the enzalutamide package insert [Appendix 9](#) for the enzalutamide formulation.

#### **5.2.2. Packaging and Labeling**

GS-5829 tablets are in white, high density polyethylene bottles with desiccant and polyester packing material. Each bottle contains 30 tablets and is enclosed with a white, continuous thread, child-resistant screw cap with an induction-sealed, aluminum-faced liner.

Study drug(s) to be distributed to centers in the US and other participating countries shall be labeled to meet applicable requirements of the United States Food and Drug Administration (FDA), EU Guideline to Good Manufacturing Practice – Annex 13 (Investigational Medicinal Products), and/or other local regulations.

Refer to [Appendix 9](#) for the enzalutamide packaging information.

#### **5.2.3. Storage and Handling**

GS-5829 tablets should be stored at controlled room temperature until required for administration. Controlled room temperature is defined as 25°C (77°F); excursions are permitted between 15°C and 30°C (59°F and 86°F). Storage conditions are specified on the label.

Until dispensed to the subjects, all bottles of study drug should be stored in a securely locked area, accessible only to authorized site personnel. The study center will be required to maintain a log of daily temperature readings in the storage area for the duration of the study. To ensure the stability and proper identification, the drug product should not be stored in a container other than the container in which it was supplied. Consideration should be given to handling, preparation, and disposal through measures that minimize drug contact with the body. Appropriate precautions should be followed to avoid direct eye contact or exposure through inhalation when handling GS-5829 tablets.

Refer to [Appendix 9](#) for enzalutamide storage and handling information.

### **5.3. Dosage and Administration of GS-5829 and Enzalutamide**

GS-5829 tablets will be provided by Gilead Sciences, Inc. and will be taken orally. Initiation of treatment with the study drug will take place after enrollment and cohort assignment. Subjects will take their dose of study drug at approximately 24-hour intervals. To reduce inter-subject variability on efficacy and safety, subjects will be instructed to take GS-5829 approximately 1 hour before or 2 hours after a meal, unless otherwise specified by protocol. Grapefruit juice is prohibited while on study drug. In one or more monotherapy dose levels or in the monotherapy expansion (Group 1), on Day 1 of Cycle 2, approximately 10 subjects may be asked to administer GS-5829 in fed state with a standardized meal (~500 to 600 calories and ~30% of calories from fat). If evaluation of food effect cannot be performed on Cycle 2, Day 1, it may be performed at a visit after Cycle 2, Day 1 (where subject has taken at least 7 consecutive days of GS-5829), if necessary.

XTANDI® (enzalutamide) will be supplied as 40 mg capsules for oral administration. Subjects assigned to receive enzalutamide in combination with GS-5829 in this study will orally self-administer 4 capsules of enzalutamide (160 mg total daily dose) once daily at approximately 24-hour intervals beginning on Study Day 1 and GS-5829 will start, at the assigned dose, 14 days ( $\pm$  3 day window) later on Cycle 1 Day 1. Subjects enrolled into Group 3 should be on at least 12 weeks of continuous enzalutamide treatment prior to starting Cycle 1 Day 1. Capsules should be swallowed whole and may be taken with or without food. Refer to [Appendix 9](#) for further details.

If the subject misses a dose, he should be instructed to take the study drug as soon as he remembers, unless more than 8 hours have elapsed since the scheduled time of the missed dose. In this case, the subject should be instructed to wait and take the next dose at the regularly scheduled time. Subjects should not take more than 1 dose of study drug at a time.

If a subject vomits within 5 minutes of dosing and the tablet is visible, the subject should be instructed to re-dose. If a subject vomits more than 5 minutes after dosing or if the tablet is not visible, the subject should be instructed to wait and take the next dose at the regularly scheduled time.

### 5.3.1. Dose Adjustment of GS-5829

In the event of a Grade 3 or 4 hematologic or any non-hematologic toxicity that the investigator considers related to GS-5829 and is clinically significant, GS-5829 will be interrupted for a maximum of 28 days until the toxicity resolves to  $\leq$  Grade 1 or returns to baseline level.

Following resolution of the toxicity or the toxicity returns to baseline level, treatment may be restarted at a reduced dose as per [Table 5-1](#). If the toxicity does not resolve or return to baseline, study drug(s) GS-5829 and enzalutamide will be permanently discontinued and the subject will return for an End of Treatment and a 30 day Safety Follow-Up visit.

No dose reduction of GS-5829 below 1.0 mg is allowed.

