### 5.3.2. Dose Adjustment in Group 2: Combination of Enzalutamide and GS-5829

Due to the CYP3A4 interaction of the two study drugs, discontinuing enzalutamide for more than 2 weeks may lead to a clinically significant increase in GS-5829 exposure. Therefore, in the event of any hematologic or non-hematologic toxicity in the combination arm, even if the toxicity is attributed by the investigator only to enzalutamide, both enzalutamide and GS-5829 may need to be interrupted or discontinued according to [Table 5-2](#).

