**Table 5-2. Dose Reduction in Group 2: Combination of Enzalutamide and GS-5829**

	Considered related to enzalutamide	Considered related to GS-5829	Considered potentially related to both enzalutamide and GS-5829 or unknown relationship
Grade 4 toxicity	Interrupt dosing of enzalutamide for at least 7 days and not longer than 17 days until symptoms improve to $\leq$ Grade 2, then resume at 120 mg. If subject is already at 120 mg, or it takes longer than 17 days to improve $\leq$ Grade 2, then permanently discontinue both enzalutamide and GS-5829.	Permanently discontinue both enzalutamide and GS-5829	Permanently discontinue both enzalutamide and GS-5829
Grade 3 toxicity	Interrupt dosing of enzalutamide for at least 7 days and a maximum of 17 days until symptoms improve to $\leq$ Grade 2, then resume at 120 mg. If subject is already at 120 mg, or it takes longer than 17 days to improve $\leq$ Grade 2, then permanently discontinue both enzalutamide and GS-5829.	Interrupt GS-5289 for a maximum of 28 days until the toxicity resolves to $\leq$ Grade 1 or returns to baseline level. Following resolution of the toxicity or the toxicity returns to baseline level, treatment may be restarted at a reduced dose as per Table 5-1 .  Enzalutamide dosing does not need to be interrupted or dose reduced.	Interrupt both enzalutamide and GS-5829 for at least 7 days and a maximum of 17 days until symptoms improve to $\leq$ Grade 1 or return to baseline level at which time subjects may resume enzalutamide at either 120 mg or 160 mg and resume GS-5829 at a reduced dose per Table 5-1 . If a subject is already at 120 mg of enzalutamide, they must discontinue.

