#### **5.4. Prior and Concomitant Medications**

Subjects who have not had a bilateral orchiectomy must be receiving androgen deprivation therapy with a GnRH analogue prior to enrollment and must continue on GnRH-analogue therapy for the duration of the study.

Abiraterone and chemotherapy are prohibited while on study drug.

Phase 1b Monotherapy: Subjects must have previously received abiraterone and/or enzalutamide.

Phase 2 Monotherapy Dose Expansion (Group 1): Subjects must have previously received enzalutamide. Subjects must not have previously received chemotherapy for mCRPC.

Phase 1b Combination Therapy Dose Escalation and Phase 2 Combination Dose Expansion (Group 2): Subjects must have previously received abiraterone, but must not have previously received enzalutamide or chemotherapy for mCRPC.

Phase 2 Combination Therapy Dose Expansion (Group 3): Subjects must have previously received enzalutamide and have been on continuous enzalutamide for the 12 weeks prior to Cycle 1, Day 1. Subjects must not have previously received chemotherapy for mCRPC. Subjects must not have previously received chemotherapy for mCRPC.

In vitro data indicate GS-5829 is a substrate of CYP3A4. Co-administration of CYP3A4 inhibitors may increase GS-5829 exposure. As such, co-administration of moderate and strong CYP3A4 inhibitors with study drug is prohibited in this study.

Co-administration of CYP3A4 inducers may decrease GS-5829 exposure. As such, moderate and potent CYP3A4 inducers are prohibited while subject is on study drug and  $\geq$  2 weeks prior to study drug administration except for subjects in Group 2 who may receive enzalutamide as described in the protocol. Examples of moderate and strong CYP3A4 inhibitors and inducers are provided in the table below.

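### After a GS-5829-related Grade 4 toxicity, Protocol 5.3.1 allows a reduced-dose restart but Table 5-2 requires stopping both drugs, and headings naming only Group 2 blur which rule binds phase 1b combination subjects

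*Protocol*

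**What the plan says.** The trigger for Protocol 5.3.1 is an "event of a Grade 3 or 4 hematologic or any non-hematologic toxicity that the investigator considers related to GS-5829 and is clinically significant". Dosing with GS-5829 is held for at most 28 days until the event falls to Grade 1 or to baseline, after which "treatment may be restarted at a reduced dose as per" Table 5-1. If the event does not resolve, "study drug(s) GS-5829 and enzalutamide will be permanently discontinued". Because that sentence names enzalutamide, the section is not, on its face, confined to monotherapy.

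Table 5-2, under 5.3.2, sets actions by severity and attribution. For a Grade 4 toxicity attributed to GS-5829, and likewise for one attributed to both drugs or of unknown relationship, the action is to "permanently discontinue both enzalutamide and GS-5829". For a Grade 4 toxicity attributed to enzalutamide, it begins "Interrupt dosing of enzalutamide for at least 7 days and not longer than 17 days".

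The heading of 5.3.2 reads "Dose Adjustment in Group 2: Combination of Enzalutamide and GS-5829", and the title of Table 5-2 carries the same Group 2 label. The text beneath the heading is wider. It speaks of what must happen "in the event of any hematologic or non-hematologic toxicity in the combination arm", and gives the CYP3A4 interaction between the two drugs as the reason.

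**The concern.** The same event leads to a permitted restart under one rule and a mandatory stop under the other, and nothing ranks them. For Group 2 a reader would take the specific table over the general section. For phase 1b combination subjects, and for the planned Group 3, the table's title does not name them, although they take both drugs.

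The risk runs one way. Stopping both drugs breaches neither rule, because 5.3.1 only permits a restart. A site that takes the headings literally could, however, put a combination subject back on GS-5829 after an event that Table 5-2 says must end treatment. The case is foreseeable in escalation, since Protocol 3.2 lists Grade 4 neutropenia among the DLTs. It also bears on reporting: SAP 4.3 summarises important protocol deviations, and whether such a restart is a deviation depends on which rule applied.

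**Working it through.** The plan states no figure on this point, so the check is mainly a reading of the rules against each other.

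**1. Which rule applies, for a clinically significant Grade 4 toxicity related to GS-5829**

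| Population | Reading by the headings | Reading by the 5.3.2 body |
|---|---|---|
| Phase 1b monotherapy, Group 1 | 5.3.1: reduced-dose restart allowed | 5.3.1: reduced-dose restart allowed |
| Group 2 | Table 5-2: stop both drugs | Table 5-2: stop both drugs |
| Phase 1b combination | 5.3.1: reduced-dose restart allowed | Table 5-2: stop both drugs |
| Group 3 (planned) | 5.3.1: reduced-dose restart allowed | Table 5-2: stop both drugs |

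Only the last two rows change with the reading.

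**2. Is the literal reading a reasonable one?** Elsewhere the protocol treats Group 2 as a phase 2 label distinct from the phase 1b combination cohorts. Section 5.4 names them side by side ("Phase 1b Combination Therapy Dose Escalation and Phase 2 Combination Dose Expansion (Group 2"), and the enzalutamide footnote in Appendix 3 lists phase 1b combination, Group 2 and Group 3 separately. Two other sentences can be taken to allow rechallenge. The recurrence sentence at the end of 5.3.2 deals with a repeat of the same Grade 3 or 4 event at the lower GS-5829 dose, which seems to presuppose a restart after Grade 4. The DLT text in 3.2 refers to a DLT that calls for dose reduction.

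**3. Which Grade 4 cells collide with 5.3.1?** Section 7.2.1 codes causality as yes wherever there is a reasonable possibility. An event possibly due to both drugs therefore also meets the 5.3.1 trigger. Two of the three Grade 4 attribution cells (GS-5829; both or unknown) require an outright stop that 5.3.1 does not.

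**4. Size of the restart.** The share of the previous dose is the Table 5-1 restart dose divided by the dose at the time of toxicity:

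- 6 to 5 mg: 5/6 = 83.3%
- 5 to 4 mg: 4/5 = 80.0%
- 4 to 3 mg: 3/4 = 75.0%
- 3 to 2 mg: 2/3 = 66.7%
- 2 to 1 mg: 1/2 = 50.0%

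Under Table 5-2 the share is 0%. The range covers only the 2 to 6 mg entries of Table 5-1. Table 3-1 goes up to 9 mg, and 3.2 lets combination dosing pass the dose found safe as monotherapy, but Table 5-1 gives no restart dose above 6 mg. The range describes dose, not likelihood of harm.

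**5. Enzalutamide-attributed toxicity.** All three severity rows in that column of Table 5-2 cap the hold at 17 days. Section 5.3.1 has no counterpart. If the headings governed, phase 1b combination subjects would have no such limit in 5.3, although 5.3.2 warns that more than 2 weeks off enzalutamide may raise GS-5829 exposure.

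**6. Lower grades.** For Grade 3 attributed to GS-5829, both rules give a hold of up to 28 days and a reduced-dose restart. For Grade 2 they differ during escalation: the Grade 2 allowance that accompanies Table 5-1 begins only after the 28-day DLT period, whereas the intolerable Grade 2 row of Table 5-2 has no such limit.

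**The case against.** The strongest reply is that the operative text already covers every combination subject. The CYP3A4 interaction exists in anyone taking both drugs, and the 5.3.2 body speaks of the combination arm. The protocol also uses Group 2 loosely. Section 5.4 exempts only Group 2 from the ban on CYP3A4 inducers, which read literally would bar phase 1b combination subjects from their assigned enzalutamide; exclusion criterion 17 says combination arms. Section 1.3 likewise describes the abiraterone-failure combination population as a second group across the whole study. Different rules for monotherapy and combination are not in themselves a contradiction.

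There are safeguards too. A 5.3.1 restart is optional and needs resolution, and recurrence at the lower dose ends treatment. Toxicities go to the Medical Monitor (7.5), who chairs the Safety Review Team that assesses each combination cohort (3.2).

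Most of this stands. Table 5-2 was probably meant for all combination subjects, and for Group 2 there is no real doubt. It does not remove the conflict: the combination arm is not defined, two titles say otherwise, 5.3.1 reaches enzalutamide by name, and the recurrence sentence inside 5.3.2 leans towards rechallenge. A mandatory stopping rule should not rest on inferred intent.

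**Conclusion.** The inconsistency is real but minor in practice. It is a fault of drafting and scope in a safety rule, affecting phase 1b combination subjects and, on paper, Group 3. SAP section 1 says that all phase 1b subjects have stopped study drug and that the study did not proceed to phase 2, so only phase 1b combination subjects could have been exposed to it. They are an unstated part of up to 72.

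Three stronger readings are tempting and not supported.

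- A reader might infer that subjects were wrongly rechallenged. The documents give no count of combination subjects treated, of Grade 4 events or of restarts.
- A reader might infer that the DLT count or MTD is compromised. The 3.2 criteria for Grade 4 neutropenia, for Grade 3 or higher thrombocytopenia and for Grade 4 non-hematologic toxicity are met by the event, not by later dosing. Nor is any effect on efficacy claimed. The SAP 7.1.6.1 summaries of interruption, reduction and discontinuation show what was actually done.
- A reader might infer that Grade 4 is the only place where the two rules part. The Grade 2 rules also differ inside the DLT window.

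The conclusion rests on the visible text. The enzalutamide label appears in Appendix 9 only as a link, and it is not assumed to settle the matter.

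**What to change.** - Retitle 5.3.2 and Table 5-2 to cover all subjects receiving GS-5829 plus enzalutamide: phase 1b combination, Group 2 and Group 3.
- State that Table 5-2 prevails over 5.3.1 for those subjects. Do not simply confine 5.3.1 to monotherapy, because Table 5-2 relies on Table 5-1 for its reduced doses. Table 5-1 and the 1.0 mg floor should continue to apply to combination subjects.
- Reword the recurrence sentence at the end of 5.3.2 so that it does not imply a restart after a Grade 4 toxicity related to GS-5829.
- State in the CSR which rule was applied to phase 1b combination subjects.

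The cost is a few lines of protocol wording and one CSR statement, with no added procedures, subjects or analyses. With dosing over, the CSR statement is the part that still has a use in this study; the wording matters if the text is reused.

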**Table 5-1. Dose Reduction of GS-5829**

Dose at time of toxicity (mg)	Restarting dose level (mg)
6	5
5	4
4	3
3	2
2	1.0

If a subject develops a recurrence of the same Grade 3 or 4 hematologic or any non-hematologic toxicity that the investigator considers related to GS-5829 and is clinically significant at the lower dose, then the subject should be permanently discontinued from all study drug(s).

After the 28 day DLT period in the Dose Escalation Phase and at any time in the Dose Expansion Phase, in the event of a Grade 2 hematologic or non-hematologic toxicity the investigator considers related to GS-5829, GS-5829 may be interrupted per the investigator's discretion for a maximum of 28 days and resumed at either the same or a lower dose per [Table 5-1](#).

Subjects who dose interrupt for a non-drug related toxicity for up to 28 days, and are deemed by the investigator to be clinically benefiting from GS-5829 prior to dose interruption, may resume GS-5829 treatment. Non-drug related dose interruptions for longer than 28 days in subjects who do not have disease progression may be considered for resumption of GS-5829 after discussion with the Medical Monitor.

